For each participant, DLT assessment will be performed during Safety Lead in part. Assessments include all toxicities observed during the initial 28-day treatment period (Cycle 1). A DLT is defined as: 
- A clinically significant AE graded according to the NCI-CTCAE version 5.0, observed during the initial 28-day treatment period following the first IMP administration.- Assessed as unrelated to underlying disease, disease progression, intercurrent illness, or concomitant medications.- At least possibly related to the IMPs (futuximab/modotuximab or trifluridine/tipiracil or both) by the investigator and meeting any of the following criteria:
• Anaemia \geq Grade 3.• Febrile neutropenia.• Uncomplicated Grade 4 neutropenia that lasts \geq 1 week.• Uncomplicated Grade 4 thrombocytopenia (less than 25,000 per mm³) that lasts \geq 1 week or any Grade \geq 3 thrombocytopenia with bleeding episodes or thrombocytopenia requiring platelet transfusion.• Grade 3 diarrhoea for >2 days despite adequate treatment or with fever and/or dehydration.• Any Grade 3 skin toxicity lasting for more than 2 weeks, or Grade 4 skin toxicity regardless of the duration¹.• Grade \geq 3 infusion-related reaction.• AST or ALT \geq 3 x ULN along with a total bilirubin > 2.0 x ULN and confirmed Hy's law cases according to FDA guidance.• Grade \geq 3 isolated AST or ALT.• Any laboratory value Grade \geq 3 with a duration \geq 3 days, considered unrelated to underlying disease, disease progression, intercurrent illness or concomitant medications/therapies.• Any other Grade 3 or Grade 4 non-haematologic AE (except for Grade 3 nausea and/or vomiting controlled by anti-emetic therapy that last less than 72 h, or Grade 3 diarrhoea responsive to anti-diarrheal medication).

¹acne, cellulitis, dermatitis acneiform, dry skin, erysipelas, erythema, folliculitis, hypertrichosis, paronychia, pruritus, rash, rash maculopapular, rash vesicular, skin exfoliation, skin hyperpigmentation and xerosis

Name of the sponsor: I.R.I.S.
Name of Finished Product: Futuximab/modotuximab (also known as S95026 or Sym004)
Name of Active Ingredient: futuximab and modotuximab
Pharmacokinetic measurements:

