4.1.3.2. DLT definition

For each participant, DLT assessment will be performed during Safety Lead in part. Assessments include all toxicities observed during the initial 28-day treatment period (Cycle 1). A DLT is defined as:

- A clinically significant adverse event (AE) graded according to the National Cancer Institute Common Terminology Criteria for Adverse Events (NCI-CTCAE) version 5.0 observed during the initial 28-day treatment period following the first IMP administration.
- Assessed as unrelated to underlying disease, disease progression, intercurrent illness, or concomitant medications.
- At least possibly related to the IMPs (Futuximab/modotuximab or Trifluridine/tipiracil or both) by the investigator and meeting any of the criteria included in [Table \(4.1.3.2\) 1](#).

Table (4.1.3.2) 1 - Dose-limiting toxicity criteria

Toxicity Class	Dose-limiting Toxicity Criteria
Haematological abnormalities	Anaemia \geq Grade 3
	Febrile neutropenia
Gastrointestinal disorders	Uncomplicated Grade 4 neutropenia that lasts \geq 1 week
	Uncomplicated Grade 4 thrombocytopenia (less than $25\ 10^9/L$) that lasts \geq 1 week or any Grade ≥ 3 thrombocytopenia (between 25 and $50\ 10^9/L$) with bleeding episodes or thrombocytopenia requiring platelet transfusion
Skin disorders	Grade 3 diarrhoea for > 2 days despite adequate treatment or with fever and/or dehydration
Infusion-related reactions	Any Grade 3 skin toxicity lasting for more than 2 weeks, or Grade 4 skin toxicity regardless of duration ¹
Hepatic abnormalities	Grade ≥ 3 infusion related reaction
Other adverse events	AST or ALT $\geq 3 \times$ ULN along with a total bilirubin $> 2.0 \times$ ULN and confirmed Hy's law cases according to FDA guidance
	Isolated AST or ALT \geq CTCAE Grade 3
	Any laboratory value Grade ≥ 3 with a duration ≥ 3 days, considered unrelated to underlying disease, disease progression, intercurrent illness or concomitant medications/therapies
	Any Grade 3 or Grade 4 non-haematologic adverse event (except for Grade 3 nausea and/or vomiting controlled by anti-emetic therapy that last less than 72h, or Grade 3 diarrhoea responsive to anti-diarrheal medication)

¹ acne, cellulitis, dermatitis acneiform, dry skin, erysipelas, erythema, folliculitis, hypertrichosis, paronychia, pruritus, rash, rash maculopapular, rash vesicular, skin exfoliation, skin hyperpigmentation and xerosis

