8.11.1. Management of treatment dose adaptations due to trifluridine/tipiracil toxicities

All toxicities related to trifluridine/tipiracil must have resolved to Grade 1 or baseline before the start of a new treatment cycle.

In the event of haematological and/or non-haematological toxicities, rules for trifluridine/tipiracil dose interruption and resumption are provided in [Table \(8.11.1\) 1](#); rules for dose modifications are provided in [Table \(8.11.1\) 2](#) and [Table \(8.11.1\) 3](#).

Treatment interruptions are regarded as lost treatment days and missed doses should not be replaced; the planned treatment schedule should be maintained.

A new treatment cycle with trifluridine/tipiracil can be started only if neutrophils count is $\geq 1.5 \times 10^9/L$ and platelets count is $\geq 75 \times 10^9/L$.

Table (8.11.1) 1 - Dose interruption and resumption criteria for haematological toxicities related to myelosuppression

Parameter	Interruption criteria*	Resumption criteria**
Neutrophils	$< 0.5 \times 10^9/L$	$\geq 1.5 \times 10^9/L$
Platelets	$< 50 \times 10^9/L$	$\geq 75 \times 10^9/L$

* Interruption criteria apply only during active treatment intake period (i.e., D1-5 and D8-12) based on an unscheduled laboratory assessment.

**Resumption criteria apply to the start of the next cycle for all participants regardless of whether or not the interruption criteria were met.

Table (8.11.1) 2 - Recommended dose modifications in case of haematological adverse event related to myelosuppression

Adverse event related to myelosuppression	Recommended dose modifications
Febrile neutropenia NCI-CTCAE Grade 4 neutropenia count $< 0.5 \times 10^9/L$ that results in more than 1 week's delay in start of next cycle	Don't start a new treatment cycle until the resumption criteria are met (Table (8.11.1) 1) When resuming dosing, decrease the dose level by 5 mg/m ² from the previous dose level (Table (6.1.3.2) 2)
NCI-CTCAE Grade 4 thrombocytopenia $< 25 \times 10^9/L$ that results in more than 1 week's delay in start of next cycle	Dose reductions are permitted to a minimum dose of 20 mg/m ² /dose twice daily Do not increase dose after it has been reduced

Table (8.11.1) 3 - Recommended dose modifications in case of non-haematological adverse event related to trifluridine/tipiracil

Adverse event related to trifluridine/tipiracil	Recommended dose modifications

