ASAT increased	> ULN – 3.0 x ULN if baseline is normal [≤ ULN]; 1.5 x baseline – 3.0 x baseline if baseline is abnormal [> ULN]	> 3.0 x ULN – 5.0 x baseline if baseline is normal [≤ ULN]; 3.0 x baseline – 5.0 x baseline if baseline is abnormal [> ULN]	> 5.0 x ULN – 20.0 x baseline if baseline is normal [≤ ULN]; 5.0 x baseline – 20.0 x baseline if baseline is abnormal [> ULN]	> 20.0 x ULN if baseline is normal [≤ ULN]; 20.0 x baseline if baseline is abnormal [> ULN]
ALAT increased	>ULN – 3.0 x ULN if baseline is normal [≤ULN]; 1.5 x baseline – 3.0 x baseline if baseline is abnormal [> ULN]	>3.0 x ULN – 5.0 x baseline if baseline is normal [≤ULN]; 3.0 x baseline – 5.0 x baseline if baseline is abnormal [> ULN]	>5.0 x ULN – 20.0 x baseline if baseline is normal [≤ULN]; 5.0 x baseline – 20.0 x baseline if baseline is abnormal [> ULN]	>20.0 x ULN if baseline is normal [≤ULN]; 20.0 x baseline if baseline is abnormal [> ULN]
ALP increased	> ULN – 2.5 x ULN if baseline is normal [≤ ULN]; 2.0 x baseline – 2.5 x baseline if baseline is abnormal [> ULN]	> 2.5 x ULN – 5.0 x baseline if baseline is normal [≤ ULN]; 2.5 x baseline – 5.0 x baseline if baseline is abnormal [> ULN]	> 5.0 x ULN – 20.0 x baseline if baseline is normal [≤ ULN]; 5.0 x baseline – 20.0 x baseline if baseline is abnormal [> ULN]	> 20.0 x ULN if baseline is normal [≤ ULN]; 20.0 x baseline if baseline is abnormal [> ULN]
Total bilirubin increased	> ULN – 1.5 x ULN if baseline is normal [≤ ULN]; 1.0 x baseline – 1.5 x baseline if baseline is abnormal [> ULN]	> 1.5 x ULN – 3.0 x baseline if baseline is normal [≤ ULN]; 1.5 x baseline – 3.0 x baseline if baseline is abnormal [> ULN]	> 3.0 x ULN – 10.0 x baseline if baseline is normal [≤ ULN]; 3.0 x baseline – 10.0 x baseline if baseline is abnormal [> ULN]	> 10.0 x ULN if baseline is normal [≤ ULN]; 10.0 x baseline if baseline is abnormal [> ULN]
Haemoglobin increased	> ULN and increase from baseline [0 ;20] (g/L)	> ULN and increase from baseline [20 ;40] (g/L)	> ULN and increase from baseline [40 ;60] (g/L)	> ULN and increase from baseline [60 ;80] (g/L)
Haemoglobin (g/L) - Anemia	[100;LLN[[80;100[< 80	
White Blood Cells (G/L) - Low	[3.0;LLN[[2.0;3.0[[1.0;2.0[< 1.0
Neutrophils (G/L) - Low	[1.5;LLN[[1.0;1.5[[0.5;1.0[<0.5
Lymphocytes (G/L) - Low	[0.8;LLN[[0.5;0.8[[0.2;0.5[<0.2
Lymphocytes (G/L) - High		[4.0;20.0]	>20	
Platelets (G/L) - Low	[75;LLN[[50;75[[25;50[<25
Prothrombin Time increased				
APTT increased	[ULN;1.5*ULN]	[1.5*ULN;2.5*ULN]	>2.5*ULN	

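### Read literally, the laboratory DLT criterion leaves the 1-week limits for uncomplicated Grade 4 neutropenia and thrombocytopenia without effect

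*Protocol*

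**What the plan says.** Protocol section 4.1.3.2 defines a DLT as a clinically significant, CTCAE-graded event in the first 28 days. It must not be due to disease, intercurrent illness or other medication. It must also be judged at least possibly related to the study drugs "by the investigator and meeting any of the criteria included in" Table (4.1.3.2) 1. Three rows matter here:

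- **Neutropenia:** "Uncomplicated Grade 4 neutropenia that lasts" 1 week or more.
- **Thrombocytopenia:** uncomplicated Grade 4 for 1 week or more. Grade 3 or higher with bleeding, or a need for platelet transfusion, also counts, with no minimum duration.
- **Laboratory values:** "Any laboratory value Grade" 3 or higher for at least 3 days. The only qualifier is an attribution condition already in the general definition.

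The synopsis gives the same thresholds. I found no rule of precedence between rows in Protocol 4.1.3.2 to 4.1.3.4, 10.1.2.6.1, 10.2 or 12.4.2, or in SAP 2.1, 3.5.1 or 7.1.

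Protocol 4.1.3.3 requires treatment to be delayed after any DLT. Table (8.11.1) 1 interrupts trifluridine/tipiracil at neutrophils below 0.5 x 10^9/L or platelets below 50 x 10^9/L. Its footnote reads "Interruption criteria apply only during active treatment intake period (i.e., D1-5 and D8-12) based on an unscheduled laboratory assessment".

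DLT incidence is one of the lead-in's primary endpoints (Table (3.4) 1). Under 4.1.3.4, enrolment halts at 3/6, 4/12, 6/18 or 8/25 participants with a DLT. SAP 3.5.1 asks for the number and percentage of participants with a DLT, and a listing.

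**The concern.** The two 1-week limits show that the authors meant to tolerate short, uncomplicated falls in counts, which are an expected effect of trifluridine/tipiracil. A separate row with a lower grade and a shorter duration, joined to the others by an any-one-is-enough rule, removes that tolerance.

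Two investigators who read the table in good faith could classify the same common event differently. The affected count is a primary endpoint, and it triggers the enrolment halts. The lead-in is also the only part that was run, so its DLT rate is a main result. A reader of the report needs to know which rule the count followed.

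**Working it through.** **1. Do the rows overlap?** Write g for the grade and d for the duration in days, for an event that has already passed the general conditions.

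- 1-week row: W = {g = 4 and d >= 7}
- Laboratory row: L = {g >= 3 and d >= 3}

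Since 4 >= 3 and 7 >= 3, every member of W is in L. So W or L equals L, and deleting the 1-week row would change no classification. For neutropenia without fever, over the 28-day window:

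| Grade | Duration (days) | 1-week row | Laboratory row | DLT under the any rule |
|---|---|---|---|---|
| 3 | 1-2 | no | no | no |
| 3 | 3-28 | no | yes | **yes** |
| 4 | 1-2 | no | no | no |
| 4 | 3-6 | no | yes | **yes** |
| 4 | 7-28 | yes | yes | yes |

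The bold entries are DLTs only through the laboratory row. The table is the same for platelets without bleeding or transfusion. The bleeding and transfusion limbs keep their effect because they also catch events of 1 to 2 days, which the laboratory row does not.

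**2. Comparison with the dosing rules.** Grades are from SAP Table (7.3) 2 (for neutrophils, the row "Neutrophils (G/L) - Low"), in 10^9/L.

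| Count | Grade 3 | Grade 4 | Interruption, Table (8.11.1) 1 | Grade 3 interrupted? |
|---|---|---|---|---|
| Neutrophils | 0.5 to <1.0 | <0.5 | <0.5 | no |
| Platelets | 25 to <50 | <25 | <50 | yes |

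For neutrophils, the dosing table lets treatment continue at Grade 3 on dosing days, while the laboratory row can make the same event a DLT with a compulsory delay. For platelets there is no such departure.

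**3. Sensitivity of the halting limits.** The plan states no target DLT rate or operating characteristics, so there is no figure to reproduce. As an illustration, assume that each of 25 participants independently has a DLT with probability p. Let S(n,k) be the probability of k DLTs among n participants with no limit yet reached. At n = 6, 12, 18 and 25, add m = 6, 6, 6 and 7 participants:

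S(n,k) = sum over x of S(n-m, k-x) x C(m,x) p^x (1-p)^(m-x)

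Mass at k >= 3, 4, 6 and 8 respectively is then removed and added up. DLT counts never fall, so checking at these four points is equivalent to watching continuously.

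| Assumed p | Expected DLTs (25p) | P(reach a limit) |
|---|---|---|
| 0.10 | 2.5 | 0.035 |
| 0.15 | 3.75 | 0.122 |
| 0.20 | 5.0 | 0.272 |
| 0.25 | 6.25 | 0.464 |
| 0.30 | 7.5 | 0.655 |

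The limits respond steeply to the rate, so the choice of rule can matter. The documents do not say where either reading falls in this table.

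**4. Can durations be recovered?** Protocol 8.2.7.1 schedules haematology at C1D1 (only if baseline is more than 7 days old), C1D15 and C2D1. Suppose Day 15 shows Grade 3 and the neighbouring values do not. The event could then have lasted any time up to just under 29 - 1 = 28 days, on either side of both the 3-day and the 1-week thresholds. Extra tests prompted by toxicity (Table (4.1.2) 1, footnote 10, and section 8.2.7) would narrow this.

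**The case against.** **The laboratory row may be residual.** In the table it appears to belong to the class of other adverse events, and so could mean laboratory values without a row of their own. That would restore the 1-week limits and is probably what was intended. But the synopsis is a flat list with no class labels. It leaves the laboratory item unqualified while marking the next item as *other*. The only stated rule is that any criterion suffices. The residual reading is possible, but nothing written secures it.

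**Only clinically significant adverse events count.** Under section 8.2.7, a laboratory abnormality must be reported as an adverse event only if it has clinical impact or is judged medically important. This will remove some Grade 3 values. It applies equally to every row, however, so it does not restore the limits.

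**A first-combination lead-in may be stricter than the dosing rules.** This stands. Grade 3 anaemia is a DLT although haemoglobin is absent from Table (8.11.1) 1. The neutrophil comparison is therefore supporting evidence, not a contradiction.

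**The consequence is mild.** This also stands. Reaching a limit pauses enrolment for an urgent DMC meeting, and the DMC weighs all the safety data.

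**A reader might extend the point to skin toxicity.** The table's last row, "Any Grade 3 or Grade 4 non-haematologic adverse event", taken alone would swallow the limit in "Any Grade 3 skin toxicity lasting for more than 2 weeks". The documents do not support calling that an error. The row appears under other adverse events, and the synopsis has "Any other Grade 3 or Grade 4 non-haematologic AE", so a residual reading is the natural one.

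**Conclusion.** As written, in both the table and the synopsis, the laboratory criterion deprives the 1-week neutropenia and thrombocytopenia limits of effect. That conclusion needs only the wording and the any-one-is-enough rule. It is worth fixing because the count is a primary endpoint and drives the halting limits.

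The direction is conservative: more DLTs and earlier pauses. The size is unknown. The nearest figures are for neutropenia of Grade 3 or higher: 34% with trifluridine/tipiracil alone (Protocol 2.8) and 55% with cetuximab added (2.3.2). A reader might use these as DLT rates, but they are not given for Cycle 1 or by duration, and they include Grade 4 events that may be DLTs under either reading. Nor should anyone infer that the DLT count ended the study: SAP section 1 gives strategic reasons.

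**What to change.** **Protocol.** In Table (4.1.3.2) 1 and the synopsis, exclude neutrophil and platelet values from the laboratory criterion, since they have their own rows. As a minor alignment, use the synopsis wording "Any other Grade 3 or Grade 4 non-haematologic AE" in the table's last row. Total white cells and lymphocytes have no row of their own and would stay under the laboratory criterion; the sponsor should confirm that this is intended.

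**SAP 3.5.1.** Because the lead-in has ended, this is the change with practical effect:

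- Show the criterion met for each recorded DLT.
- List Cycle 1 drug-related neutrophil and platelet events of Grade 3 or higher lasting at least 3 days, each flagged as DLT or not, so that the count can be read under either rule.
- Note that durations may be imprecise, because Day 15 is the only scheduled haematology sample between C1D1 and C2D1.

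The planned adverse event listings and Cycle 1 worst-value summaries hold part of this information, but the plan does not say that they link grade, duration and DLT status. The listing templates are in a separate document and may already show the criterion.

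**Cost.** Small wording edits, one column and one listing, all from data already collected. If the DLT form does not record the row met, the sponsor can assign it from the adverse event record.

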Participants who meet any following criteria will not be evaluable for DLT and therefore will be replaced during the Safety Lead-In part of the study.

- Permanently discontinued treatment during DLTs assessment period for reasons other than DLT.
- Did not undergo a DLT assessment at the end of Cycle 1.
- Participants must complete at least the first cycle of treatment with a dose intensity [(administered dose in mg/planned dose in mg) x 100] higher than 75% with a minimum follow-up duration of 28 days. The dose intensity for single-agent trifluridine/tipiracil in Phase 3 studies is approximately 89%; therefore, for the combination a value of 75% is considered appropriate. Participants who require a dose interruption or reduction during the initial 28-day treatment period (Cycle 1) will remain evaluable for tolerability decisions if the reason for the reduction and/or interruption is a DLT. Participants will be replaced if they have received fewer than 75% dose intensity of trifluridine/tipiracil or futuximab/modotuximab for any reason other than an AE or abnormal laboratory value that is not related to their disease, disease progression, intercurrent illness or concomitant medications/therapies.

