4.1.3.3. DLT management

Study treatments must be delayed for any participant who experienced a DLT. Conditions to resume treatment are described in [Section 8.11](#).

All DLT will be reported to I.R.I.S. within 24 hours via DLT form in the e-CRF. After having filled in the DLT form, fill in the "Adverse Event" page of the e-CRF, without waiting for the results of the clinical outcome or of additional investigations. When data of the DLT form are submitted, an e-mail will be immediately and automatically sent to the sponsor.

If the e-CRF is unavailable when the investigator is informed of the DLT, he/she should:

- Report the DLT on a paper "DLT form".
- Send the form immediately to I.R.I.S. at the following e-mail address [contact], with local project manager and monitor in copy

As soon as the e-CRF becomes available, the investigator must enter the data in the e-CRF.

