6.1.1.3. Schedule

- Once weekly on Day 1, Day 8, Day 15, and Day 22 (\pm 2 days) of each cycle (4 weeks [28 days] equals 1 dosing cycle).

A weekly dosing schedule is to be maintained, unless delay is required to allow for amelioration of toxicities (or in the event of scheduling difficulties associated with extended weekends, holidays, etc.). Futuximab/modotuximab should be administered after trifluridine/tipiracil intake.

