6.1.3.2. Schedule

- Trifluridine/tipiracil should be administered before futuximab/modotuximab administration.
- Trifluridine/tipiracil should only be given on Days 1 through 5 and Days 8 through 12 of each cycle. If doses are missed or held on those days, the participant should not make up for missed doses. Extension of study treatment into Days 6 to 7 or into the rest period (Days 13 through 28) is not permitted.
- Trifluridine/tipiracil should be taken with a glass of water within 1 hour after completion of morning and evening meals (or in accordance with the local SmPC of trifluridine/tipiracil).
- Any missed doses reported by the participant should be recorded in the e-CRF.
- Trifluridine/tipiracil dosage is calculated according to BSA (Body Surface Area). Table (6.1.3.2) 1 shows the number of tablets that are needed per calculated BSA for a dose of 35 mg/m². Table (6.1.3.2) 2 shows the number of tablets that are needed per calculated BSA for a reduced dose (30 mg/m², 25 mg/m² and 20 mg/m²). The BSA will be calculated by the site (in Safety Lead-In part) or IWRS (in Randomised part) using the following DuBois formula³⁰ all BSA calculations are rounded to 2 decimal places): BSA (m²) = ([Body Weight (kg)]^{0.425} x [Height (cm)]^{0.725}) x 0.007184.
- If at the beginning of the new treatment cycle, a participant's body weight decreases by $\geq 10\%$ from baseline, the site (in Safety Lead-In part) or IWRS (in Randomised part), will recalculate the participant's BSA and adjust trifluridine/tipiracil dosage.
- In case of change of dose level in Randomised part, the IWRS will provide the study site with the adjusted trifluridine/tipiracil dosage.
- No increase in trifluridine/tipiracil dose due to increase in BSA is permitted.

Table (6.1.3.2) 1 - Number of tablets of trifluridine/tipiracil per dose (standard dose) according to body surface area

Trifluridine/tipiracil Dose (2 x daily)	BSA (m ²)	Dosage in mg (2x daily)	Total daily dose (mg)	Tablets per dose (2x daily)	
				15 mg/6.14 mg	20 mg/8.19 mg
35 mg/m ²	< 1.07	35	70	1	1
	1.07 - 1.22	40	80	0	2
	1.23 - 1.37	45	90	3	0
	1.38 - 1.52	50	100	2	1
	1.53 - 1.68	55	110	1	2
	1.69 - 1.83	60	120	0	3
	1.84 - 1.98	65	130	3	1
	1.99 - 2.14	70	140	2	2
	2.15 - 2.29	75	150	1	3
	≥ 2.30	80	160	0	4

BSA = body surface area (calculate to 2 decimal places)

Table (6.1.3.2) 2 - Number of tablets of trifluridine/tipiracil per dose (reduced dose) according to body surface area

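### The DLT evaluability rules conflict for a participant with a DLT who dies or is lost in Cycle 1, some related deaths fall outside the DLT definition, and the SAP counts DLTs only in the evaluable set

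*Protocol*

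**What the plan says.** Protocol 4.1.3.2 opens its evaluability list with "Participants who meet any following criteria will not be evaluable for DLT and therefore will be replaced". Three bullets follow.

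- First bullet: "Permanently discontinued treatment during DLTs assessment period for reasons other than DLT". Stopping because of a DLT is exempt.
- Second bullet: "Did not undergo a DLT assessment at the end of Cycle 1". There is no exemption.
- Third bullet: at least one cycle at more than 75% dose intensity, "with a minimum follow-up duration of 28 days". The follow-up requirement has no exemption. The same bullet adds that a participant whose Cycle 1 dosing was interrupted or reduced "will remain evaluable for tolerability decisions if the reason for the reduction and/or interruption is a DLT".

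Protocol 4.1.3.3 adds: "Study treatments must be delayed for any participant who experienced a DLT".

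The last row of Table (4.1.3.2) 1, and its counterpart in the synopsis, make other non-haematologic events a DLT at Grade 3 or Grade 4. Protocol 8.8 grades severity from 1 to 5, with Grade 5 for a death related to the event.

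Protocol 4.1.3.4 states its DLT limits for evaluable participants: 3/6, 4/12, 6/18 and 8/25.

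SAP 2.1 defines the DLT Evaluable Set as Safety Set participants who are evaluable for DLT and does not say what evaluable means. SAP 3.5.1 summarises and lists DLTs in that set only, under a label (DLTS) that differs from the one defined (DLTES). Protocol 10.1.1.1 defines no DLT-evaluable analysis set and assigns all Safety Lead-In analyses to the Safety Set. Protocol 10.1.2.6.1 lists the DLT summary for the Safety Lead-In with no restriction to evaluable participants.

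**The concern.** DLT incidence is the first primary endpoint listed for the Safety Lead-In in Table (3.4) 1. SAP section 1 says the Randomised part was cancelled for strategic reasons, so the lead-in is the only part analysed.

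A non-evaluability rule is meant to remove participants who tell us nothing about DLTs. A participant who has already had a DLT has given the answer, whatever follow-up comes after. If the rule can remove that participant, and replacement supplies someone without a DLT, the count and percentage fall. The cases at risk are the most severe: those who die or are lost within the 28-day window. A DLT definition that leaves some related deaths unclassified works in the same direction.

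At stake are the reported DLT count and percentage and, while enrolment was running, the reading of the numeric limits.

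**Working it through.** **Step 1: the evaluability sentences applied to one case.** Take a participant with a DLT on Day 10 who dies on Day 20.

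- Interruption sentence, third bullet: 4.1.3.3 required treatment to be delayed, so dosing was interrupted because of a DLT. The participant stays evaluable.
- First bullet: if the DLT is what ended treatment, the reason is a DLT. The participant is not removed.
- Second bullet: no end-of-Cycle-1 DLT assessment took place. The participant is removed and replaced.
- Follow-up requirement, third bullet: 20 days is less than 28. The participant is removed.

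Meeting any one criterion suffices, so a literal reading removes the participant, while the interruption sentence says the opposite. No sentence sets a priority. The closing sentence of the third bullet, on adverse events as a reason for low dosing, concerns dose intensity only and does not settle the matter. A participant followed to Day 28 and assessed is unaffected.

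**Step 2: the DLT rows against the five-grade scale.**

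| Row in Table (4.1.3.2) 1 | Can it include Grade 5? |
|---|---|
| Anaemia, infusion-related reaction, isolated AST/ALT, laboratory values, thrombocytopenia with bleeding | Yes: worded as Grade 3 or above |
| Febrile neutropenia | Yes: no grade limit |
| Diarrhoea | Names Grade 3 only |
| Skin | Names Grades 3 and 4 only |
| Catch-all, non-haematologic | Names Grades 3 and 4 only |

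What is left is a related fatal non-haematologic event with no earlier qualifying Grade 3 or 4 phase and no other applicable row. Protocol 2.6 names skin infections and gastro-intestinal disorders as the combination's potential risks, and the rows closest to those stop below Grade 5. The two gaps can compound: if such a death is not a DLT, treatment ended for a reason other than DLT, and the first bullet could then also remove that participant.

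**Step 3: SAP against protocol.** The protocol places the DLT summary in the Safety Set (10.1.1.1 with 10.1.2.6.1). SAP 3.5.1 narrows it to a set whose membership depends on the unresolved rule in Step 1.

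**Step 4: size for one case.** The documents give no DLT rate or operating characteristics for the lead-in, so there is no stated figure to reproduce. The inputs are the limits k of n in Protocol 4.1.3.4. Suppose k participants have a DLT, and one of them is removed and replaced by a participant without a DLT. The rate reads (k − 1)/n instead of k/n, a fall of 1/n.

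| Limit | DLT participant kept | One removed and replaced | Fall (percentage points) |
|---|---|---|---|
| 3/6 | 50.0% | 2/6 = 33.3% | 16.7 |
| 4/12 | 33.3% | 3/12 = 25.0% | 8.3 |
| 6/18 | 33.3% | 5/18 = 27.8% | 5.6 |
| 8/25 | 32.0% | 7/25 = 28.0% | 4.0 |

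The comparator is k/n because a participant kept as evaluable would not have been replaced. In each row the single removal takes the count from the halting limit to one below it. If the replacement also has a DLT, the count stays at k.

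**The case against.** The intent of 4.1.3.2 is easy to see. It spares a DLT in two places, and a sensible sponsor would count a participant who died of a DLT. That stands as evidence of intent. It does not remove the second bullet or the 28-day requirement, which carry no such exemption.

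A reader might infer a separate unprotected window at the end of the cycle. The antibody mixture is given "Once weekly on Day 1, Day 8, Day 15, and Day 22", and "Trifluridine/tipiracil should only be given on Days 1 through 5 and Days 8 through 12 of each cycle", so after Day 22 no Cycle 1 dose remains to interrupt. The documents do not support treating this as a distinct defect. A death from a DLT in those days still ends treatment because of a DLT, which the first bullet spares. It is the same wording conflict.

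On deaths, Protocol 4.1.3.3 requires DLTs to be reported within 24 hours, and the adverse event page is completed before the outcome is known. A fatal event that passed through a qualifying Grade 3 or 4 phase would therefore be captured as a DLT first. This narrows the gap to the residual case in Step 2 but does not close it.

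Finally, the effect on decisions is limited. DLTs are monitored continuously, and the DMC reviews all safety data and can stop enrolment at any time. The SAP tabulates related treatment-emergent events leading to death in the Safety Set and lists deaths. All of this stands. These safeguards would expose such a case, but they do not correct the DLT count or percentage.

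**Conclusion.** The point holds as a conflict in the evaluability wording, a residual gap in the DLT definition, and an SAP restriction that the protocol does not make. For one removed DLT participant replaced by one without a DLT, the reported rate falls by 4.0 percentage points at 25 participants and by 16.7 at 6. That assumes the literal criterion is applied and the removed DLT is not kept in the count. If a DLT is counted when reported and never taken out, halting is unaffected. If no such event occurred, nothing changes, and the documents show none.

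A reader might infer that fatal DLTs were certain to be dropped, or that enrolment decisions were wrong. The documents support neither: exclusion is one of two readings, and the DMC was not bound to the numeric limits. Nor can a probability be attached to such a loss. The only loss figure is the 7% lost to follow-up in Protocol 10.2, which is for the Randomised part and does not describe Cycle 1 of the lead-in. What remains at risk is the reported primary endpoint, not safety oversight as a whole.

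**What to change.** 1. Reconcile the criteria in Protocol 4.1.3.2, and repeat the result in SAP 2.1, so that a participant with a DLT in the 28-day window is DLT-evaluable and the non-evaluability criteria apply only to participants without a DLT.
2. Reconcile the catch-all row, in the table and the synopsis, with the five-grade scale in Protocol 8.8, so that the classification of related deaths is stated.
3. Align SAP 3.5.1 with Protocol 10.1.1.1 and 10.1.2.6.1: summarise and list all DLTs in the Safety Set next to the evaluable-set result, and use one label for the evaluable set.

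The cost is protocol and SAP wording, one table and one listing. No new data are needed. With enrolment over, the first two items can only affect how cases are classified in the report. The third is useful whichever reading was applied, because it shows any DLT that the evaluable set leaves out.
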